6.6 Prior and Concomitant Medications

6.6.1 Prohibited Medications

All participants may receive therapy for HC with cidofovir (IV or through intravesical instillation), fluoroquinolones (eg, ciprofloxacin), or leflunomide, provided that these agents are initiated prior to randomization. Initiation of these agents for the treatment of HC during the first 6 weeks is prohibited. These agents should not be discontinued during the first 6 weeks after randomization unless needed to manage toxicity. Dose changes should not be made during the first 6 weeks unless needed for renal dose adjustment.

Use of cidofovir during the first 6 weeks of the study for the treatment of non-HC-associated AdV or another non-HC viral infection is permitted, but should be discussed with the Medical Monitor.

Receipt of other investigational antiviral treatments (eg, brincidofovir) \leq 7 days prior to randomization and throughout the duration of the study is prohibited.

T cell ablative therapies, such as antithymocyte globulin, alemtuzumab (Campath-1H), or other immunosuppressive T cell-targeted monoclonal antibodies, are prohibited during the study. Use of corticosteroids ≥0.5 mg/kg/day prednisone (or equivalent) should not be administered during the study unless clinically required.

COVID-19 vaccination should be avoided for at least 28 days following the second infusion of study treatment (PSL or placebo) when feasible to minimize confounding due to the possible overlap of adverse effects (see Section 1.5.3).

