A supportive analysis of the primary efficacy endpoint will also be conducted, using a Cox proportional hazards model in order to account for additional potential confounders of the treatment effect. The Cox model will include fixed effect terms for randomized treatment assignment, the randomization stratification factors, concomitant antiviral use, and concomitant systemic corticosteroid use.

In addition, analysis of the primary efficacy endpoint will also be performed based on the BK mITT and BK PP Populations as sensitivity analyses. Subgroup analyses will be conducted to compare responses in participants with BKV viruria $<10^7$ copies/mL to those with BK viruria $\ge10^7$ copies/mL, and to evaluate responses in participants who receive concomitant antiviral therapies to those who do not receive these therapies during the study.

If the result of the primary efficacy endpoint (ie, time to resolution of macroscopic hematuria) is statistically significant based on the BK ITT Population, a formal hypothesis test will be conducted sequentially of this same endpoint based on the overall ITT Population using a 0.025 significance level, rather than the Pocock-adjusted 0.0147 significance level used for the primary analysis based on the BK ITT Population. A sensitivity analysis will also be conducted based on the overall mITT Population.

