3.1.5 Strata and Covariates

Randomization will be stratified by

. If there are

discrepancies in stratification factor values between the IRT and the EDC database, the values recorded in the EDC database will be used for all the analyses in this SAP. For deriving cidofovir use within 4 weeks prior to screening or during the screening process, such medication is taken within 4 weeks prior to screening visit through the randomization date.

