3.3.5 Prior and Concomitant Medications

Prior and Concomitant medications will be collected starting 30 days before screening and coded to anatomical therapeutic chemical (ATC Level 2) class and preferred term using the WHODrug Dictionary. All medications taken prior to the first dose of study treatment will be considered as prior medications. The medications taken prior to the first dose of study treatment and were ongoing or started on or after the first dose of study treatment will be considered as concomitant medications.

The numbers and percentages of participants taking prior and concomitant medications by ATC class and preferred term will be summarized by treatment group and in total based on the Safety Population.

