3.4 Efficacy Analyses

3.4.1 Primary Efficacy Endpoint

The primary endpoint is the time to resolution of macroscopic hematuria in participants with documented BK viruria. Resolution of macroscopic hematuria is defined as resolution to Grade 0 or 1 on the Bedi scale on 2 consecutive urine assessments \geq 2 days apart without continuous bladder irrigation or nephrostomy tubes that are uncapped; Grade 1 requires confirmation of resolution by urinalysis results of \leq 100 RBCs/HPF. If a participant has nephrostomy tubes that are capped, Bedi assessments may be performed on urine voided through the urethra or a bladder catheter (eg, Foley or suprapubic catheter), including for the purpose of assessing for resolution.

If the Bedi grade at randomization is missing, then the most recent screening Bedi grade will be used if available. If there are no Bedi grades at either randomization or during screening, the participant will be assumed to be eligible. The primary efficacy analysis will be conducted after all participants have completed 24 weeks of follow up or discontinued from the study. At the primary analysis, the PSL group will be compared to the placebo group in the BK ITT Population using a stratified log-rank test adjusting for stratification factors at randomization (derived based on EDC data). The study will be considered a success if the one-sided p-value from the stratified log rank test comparing treatment to control is less than 0.025. A stratified Cox proportional hazards model will be conducted to produce the hazard ratio of the treatment effect.

Time to resolution will be calculated starting from the date of randomization to the date of the first visual urine assessment without macroscopic hematuria (by the Hemostick® visual scale with score of 0 for outpatients; by the Bedi scale with a Grade 0 or 1 for inpatients) will be used, but 2 consecutive Bedi grades of 0 or 1 are required to establish resolution as noted above. If an outpatient does not have a Hemostick score at the time of resolution, the first of the 2 consecutive Bedi grades of 0 or 1 will be used for determining the time to resolution, which is the same approach being applied to inpatients. For inpatients who resolve on the date of hospital discharge, the Bedi grade scored on the discharge date will be used for determining time to resolution if available; if no Bedi grade is available at the time of discharge, then the Hemostick score will be used.

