Sensitivity Analysis	BK ITT	Same as primary	A stratified Cox model including fixed effect terms for randomized treatment assignment, concomitant antiviral use, and concomitant systemic corticosteroid use.		
Supportive 1	BK mITT	Same as primary	Same as primary		
Supportive 2	BK PP	Same as primary	Same as primary		
Supportive 3	mITT	Same as primary	Same as primary		

Subgroup analyses will be conducted for the BK ITT population to compare the primary endpoint by baseline BKV viruria (<10⁷ copies/mL vs \geq 10⁷ copies/mL), demographic characteristics (eg, age group, sex), stratification factors (derived based on EDC data), and use of concomitant antiviral therapies with potential activity against BK virus during the study. Such agents include cidofovir, ciprofloxacin, and leflunomide. The subgroup analysis will also be conducted by the number of HLA matches and class of HLA matches (class I/II/both).

Analysis will be performed excluding participants who did not have a Bedi Grade ≥2 at randomization from the BK ITT and BK mITT.

All the time to event primary efficacy endpoints will be presented using Kaplan-Meier plots. The estimated median time to event with the corresponding 95% confidence intervals will be presented by treatment group.

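### The antiviral subgroup and the sensitivity Cox model should use antiviral and steroid status before randomisation, not use after it

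*SAP*

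**What the plan says.** The SAP (3.4.1) lists a subgroup of the primary endpoint by "use of concomitant antiviral therapies with potential activity against BK virus during the study" and names cidofovir, ciprofloxacin and leflunomide. Protocol 9.2.1.1 has the same subgroup, to "evaluate responses in participants who receive concomitant antiviral therapies to those who do not receive these therapies during the study".

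The sensitivity row of the SAP estimand table specifies "A stratified Cox model including fixed effect terms for randomized treatment assignment, concomitant antiviral use, and concomitant systemic corticosteroid use". Protocol 9.2.1.1 gives the reason for such a model: "in order to account for additional potential confounders of the treatment effect". Neither document ties the two medication terms to a time point. The SAP's only definition of concomitant, in 3.3.5, was written for the medication tables. It covers drugs ongoing at first dose as well as those "started on or after the first dose of study treatment will be considered as concomitant medications".

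Three other places bear on the point:

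- Protocol 6.6.1, on cidofovir, fluoroquinolones and leflunomide: "Initiation of these agents for the treatment of HC during the first 6 weeks is prohibited". It sets no such bar after that.
- SAP 3.1.5 has a pre-randomisation rule, for cidofovir only: "such medication is taken within 4 weeks prior to screening visit through the randomization date".
- SAP 3.4.1 also plans an HR without these covariates: "A stratified Cox proportional hazards model will be conducted to produce the hazard ratio of the treatment effect".

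**The concern.** After Week 6, a participant who starts one of these agents for HC is someone whose HC still needs treatment. Being a user therefore depends partly on not having resolved, and that is commoner in the arm that resolves more slowly. The non-user group loses slow resolvers, more of them from the slower arm, so its HR is pulled toward 1.

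Steroids have a related problem. The protocol allows them for inflammatory reactions due to the product (1.5.1), as part of standard GVHD treatment (8.11) or when clinically required (6.6.1). Their use can therefore be a consequence of assigned treatment.

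A variable that follows from treatment or outcome does not confound a randomised comparison, and adjusting for it changes the quantity estimated. The sensitivity row keeps the primary intercurrent-event strategy, and neither drug class is listed as an intercurrent event, so the model no longer checks the primary estimand. At stake is how one subgroup result and one sensitivity HR are read. An apparent interaction, or a gap between adjusted and primary HRs, could arise with no antiviral effect at all.

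**Working it through.** **Inputs from SAP 2.2.3.** Median resolution 12 weeks (placebo) and 6 weeks (PSL), exponential times; 24 weeks of follow-up; 20% dropout by Week 24, exponential and equal by arm; N = 105; one-sided 0.025. **Assumed:** 1:1 allocation (the ratio is redacted).

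**The plan's own power figure.** The hazards are ln2/12 = 0.0578 and ln2/6 = 0.1155 per week, and dropout is −ln(0.8)/24 = 0.0093. With resolution hazard λ and dropout hazard μ, P(event) = λ/(λ+μ) × [1 − exp(−24(λ+μ))].

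- Placebo: 0.861 × 0.80 = 0.689. PSL: 0.926 × 0.95 = 0.879.
- Events: 52.5 × (0.689 + 0.879) = 82.3.
- Power: Φ(√(82.3/4) × ln2 − 1.96) = Φ(1.18) = 88.2%, against 86.4% stated, with no futility loss modelled. That is close enough to use these inputs.
- SE of log HR: about 2/√82.3 = 0.22; simulated 0.22 to 0.24. I use 0.23.

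**Why use differs by arm.** At Week 6 the share unresolved is 2^(−6/12) = 71% on placebo and 2^(−6/6) = 50% on PSL, ignoring dropout. Assume 20% use at randomisation and that 70% of those still unresolved start for HC at a uniform time in Weeks 6 to 14. The mean probability of being unresolved and on study at the start time is [exp(−6h) − exp(−14h)]/(8h), with h = λ+μ. This gives 0.52 on placebo and 0.30 on PSL. Use during the study is then 0.20 + 0.80 × 0.70 × 0.52 = 49% on placebo and 0.20 + 0.80 × 0.70 × 0.30 = 37% on PSL, with a drug that does nothing.

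**Simulation (inert antiviral, true HR 2, no interaction).** The main set had 20% baseline use, HC starts of 10 to 70% in Weeks 6 to 14, and non-HC starts of 0 to 20% at any time (200,000 participants per scenario). A second set (40,000 per scenario) included an extreme case: 10% baseline use and 90% HC starts in Weeks 6 to 8.

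| HC / non-HC starts | Unadjusted HR | Adjusted, use during study | Adjusted, baseline use | Users | Non-users |
|---|---|---|---|---|---|
| 10% / 10% | 1.989 | 1.987 | 1.989 | 2.04 | 1.96 |
| 70% / 0% | 2.015 | 1.901 | 2.015 | 2.19 | 1.69 |
| 90% / 0% (extreme) | – | 1.78 | 1.98 | 2.03 | 1.43 |

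- Across the main set, HRs were 2.02 to 2.19 in users and 1.97 to 1.69 in non-users. The adjusted HR fell by 0.00 to 0.11.
- Shift in the adjusted HR: ln(2.015/1.901) = 0.058, and 0.058/0.23 = 0.25 SE. In the extreme case, ln(1.98/1.78) = 0.106, or 0.46 SE.
- Subgroup gap at 70%: ln(2.19/1.69) = 0.26 against an SE of the difference of 0.46 to 0.52, so 0.5 to 0.6 SE. In 1,500 simulated trials of N = 105 in each of six scenarios, the interaction reached p < 0.05 in 6.0 to 9.3%.
- The inert drug's own adjusted HR was 0.38 at 70% uptake and 0.84 at 10%: it would appear to delay resolution.
- With a true treatment HR of 1, adjusted and unadjusted HRs agreed within 0.003.
- With pre-randomisation coding, subgroup HRs were 1.97 to 2.03 (users) and 1.98 to 2.01 (non-users).
- Allocation of 2:1 gave the same pattern.

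**Steroids: direction only.** Suppose steroids start from Week 2 at 0.03 per week on placebo and halve the resolution hazard; both are assumptions. If the start rate is equal by arm, the treatment HR moves from 1.95 to 1.89 on adjusting for use during the study. If it is doubled on PSL, the HR moves from 1.84 to 2.23.

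**The case against.** The strongest reply is that this matters little. The shift in the adjusted HR is a fraction of a standard error and toward 1, no benefit is manufactured under the null, and an HR without these terms is already planned. The larger figures need high uptake after Week 6, which neither document gives. All of that stands and sets the priority. It also cuts the other way: the 0.25 SE ceiling belongs to the assumed 70% uptake, and at 90% it is 0.46 SE.

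Protocol 6.6.1 also says these agents should not be stopped in the first 6 weeks except for toxicity. For HC use, early on-study status is therefore close to pre-randomisation status. That is true, and it confines the antiviral problem mainly to later starts.

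The Cox half is conditional. Concomitant is not defined for the model, and its antiviral term is not limited to BK-active agents, some of which would be used for reasons unrelated to HC. A time-dependent term would remove most of the late-start artefact, since everyone in a risk set is unresolved, but the SAP does not specify one. It would also still adjust away any steroid use caused by treatment. The subgroup wording allows no baseline reading.

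Finally, if cidofovir is a redacted stratification factor, a baseline antiviral subgroup will overlap the stratification-factor subgroup already planned. That is a fair cost of the change.

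**Conclusion.** The concern holds. The subgroup is explicitly defined by use after randomisation, and the Cox covariates are left open to it. With an inert antiviral and a constant HR of 2, the subgroup would on average show a larger effect in users than in non-users (from 2.02 against 1.97 up to 2.19 against 1.69). The adjusted HR would be lower by up to 0.11. These sizes rest on 1:1 allocation, 20% baseline use and 10 to 70% late uptake, none of them in the documents. The steroid term could move the HR either way by an unknown amount.

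The effect is small against sampling error at N = 105. The primary test, alpha, sample size and power do not change. It should be corrected because a sensitivity analysis that can depart from the primary result for reasons unrelated to robustness cannot do its job, and the correction is cheap.

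**What to change.** In the sensitivity row of SAP 3.4.1, specify: *a stratified Cox model with terms for randomised treatment, antiviral use before randomisation (yes/no), and systemic corticosteroid use ongoing at the randomisation date (yes/no).* Define antiviral use by the window that SAP 3.1.5 gives for cidofovir, label it prior use rather than current use, and list the agents that count. If cidofovir is a stratification factor, let the term cover the other agents.

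Replace the subgroup with: *use before randomisation, in the same window, of cidofovir, ciprofloxacin or leflunomide (yes/no).* Report antiviral and steroid use during the study by arm, descriptively only.

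Align the Cox and subgroup sentences of protocol 9.2.1.1 at the next amendment. The Cox models in SAP 3.4.2 and 3.4.3, whose covariates are not named, should follow the same rule.

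The cost is two SAP sentences and two protocol sentences, plus that alignment. No new data are needed: medications are collected from 30 days before screening (SAP 3.3.5), which covers the 4-week window, and their dates are on the eCRF (protocol 6.6.3). Two downsides: a protocol-named subgroup is redefined, and the baseline steroid term can capture only doses allowed at entry. No rule on permitted medicines changes.

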3.4.2 Key Secondary Efficacy Endpoint

The key secondary endpoint is the time to resolution of bladder pain as measured by age appropriate COAs. Resolution of pain is defined as participants achieving a score on the relevant COA that does not exceed "mild pain" (defined in Protocol Section 7), confirmed with 2 consecutive scores, without use of prescription pain medications (not PRN or "as needed) or supportive bladder care. The relevant COA is the worst daily pain (ie, the participant's worst bladder pain over the previous 24 hours), which is recorded daily for the first 6 weeks of the study and once weekly thereafter. Intermittent missing scores will be omitted.

The analysis will include all the participants whose pain scores exceed "mild pain" at randomization or who use prescription pain medications (not PRN or "as needed") or supportive bladder care at randomization, assuming their bladder pain scores exceed mild. If the scores at randomization are missing, a prior pain score will be used if available. Otherwise, the participant will not be included in the analysis.

Time to resolution will be calculated from the date of randomization to the date of the first resolution of bladder pain. Participants not observed to achieve resolution will be considered censored at their last follow up. The pain scores collected while participants use pain medications (not PRN or "as needed") or supportive bladder care will not be used.

If the result of the analyses of the primary efficacy endpoint is statistically significant based on both the BK ITT and overall ITT Populations, a formal hypothesis test will be conducted sequentially of the time to resolution of bladder pain based on the BK ITT Population in the same manner as described for the primary efficacy analysis of the primary efficacy endpoint, and a one-sided 0.025 significance level will be used. If this result of the analysis of time to resolution of bladder pain based on the BK ITT Population, a formal hypothesis test of this endpoint will then be conducted based on the overall ITT Population using a 0.025 significance level.

A sensitivity analysis of the key secondary efficacy endpoint will also be conducted for the BK ITT population, using a Cox proportional hazards model in order to account for additional potential confounders of the treatment effect. In addition, supportive analyses of the key secondary efficacy endpoint will also be performed based on the BK mITT, BK PP and mITT Populations.

Secondary efficacy endpoint in the estimand framework is described as follows:

Statistical category	 Estimand: Treatment: Study Treatment (PSL) or Placebo Population: Pediatric and adult participants with virus-associated hemorrhagic cystitis following allogeneic HCT Endpoint (Variable): Time to resolution of bladder pain as measured by age appropriate COAs. Resolution of pain is defined as participants achieving a score on the relevant COA that does not exceed "mild pain" (defined in Protocol Section 7), confirmed with 2 consecutive scores, without use of prescription pain medications (not PRN or "as needed") or supportive bladder care. Intercurrent events: Include intercurrent events from primary efficacy endpoint and 1. Use of prescription pain medications (not PRN or "as needed") or supportive bladder care 2. Early discontinuation from the study treatment before achieving resolution 3. Death due to any cause before achieving resolution 4. Missing daily or weekly assessment of bladder pain 5. Treatment for hemorrhagic cystitis with non-PSL VSTs before achieving resolution 		
	resolution Analysis set Intercurrent event handling Population-le		
	-	strategy	summary (Analysis):
Secondary	BK ITT	 Composite strategy: Data collected while on ICE 1 will not be used for the key secondary endpoint, ie, assuming using ICE 1 is equivalent to pain exceeds "mild pain." Treatment policy strategy: Data collected after occurrence of ICE 2 will be used for the key secondary endpoint. Composite strategy: Participants with ICE 3 will be censored at the last follow-up time of any participant. Hypothetical strategy: ICE 4 will be omitted and next observed assessment will be used Composite strategy: Participants with ICE 5 will be considered treatment failures for the key secondary endpoint of time to resolution of bladder pain and will be censored at the last follow-up time of any participant. 	As primary but using a one-sided 0.025 significance level.
Supportive 1	BK mITT	Same as secondary	Same as secondary
Supportive 2	mITT	Same as secondary	Same as secondary

Subgroup analyses may be conducted for the BK ITT population for age appropriate COAs to evaluate responses in participants who took different outcome measurements, similar to the primary efficacy endpoint.

3.4.3 Other Efficacy Endpoints

If the result of the key secondary efficacy analyses based on the BK ITT and overall ITT Populations are both statistically significant, a formal hypothesis test will be conducted sequentially of the first other secondary endpoint, number of days in the hospital, based on the BK ITT Population. The analysis will be performed using a linear regression model with terms for treatment and the stratification factors at randomization (defined based on EDC data). This secondary endpoint will be tested at the one-sided 0.025 alpha level. If the result of the analysis based on the BK ITT Population is statistically significant, a formal hypothesis test of this endpoint will be conducted based on the overall ITT Population using a 0.025 alpha level. Supportive analyses will be conducted using the BK mITT, BK PP, and mITT Populations.

The sequential testing described above will control the overall Type I error for these endpoints at the one-sided 0.025 level.

Other continuous and categorical efficacy endpoints (including secondary and exploratory endpoints not selected for hierarchical testing above) will be summarized descriptively by treatment group using appropriate populations. Categorical endpoints will be summarized using the number and percentage of participants within each category.

Time-to-event endpoints will be summarized using Kaplan-Meier estimates. Treatment comparison using a stratified log-rank test adjusted by stratification factors at randomization (defined based on EDC data) at one-sided significance level 0.025 will be reported as well. In addition, the hazard ratio along with the 95% confidence intervals for the true hazard ratio will be calculated using a stratified Cox proportional hazards model with treatment, and other potentially confounding factors.

There is no adjustment for multiplicity in the analyses of these other efficacy endpoints.

Specifically, the following efficacy endpoints will be analyzed based on BK ITT Population unless mentioned otherwise, and equally at the one-sided 0.025 level.

Time to resolution of viremia for each target virus (ie, BKV, AdV, CMV, HHV-6, JCV, and/or EBV) over the 24-week study period (only for participants with detectable viremia at randomization) will be analyzed using Kaplan-Meier estimates, and treatment effect will be compared using stratified log-rank test and hazard ratio with stratified Cox proportional model. Evaluation of this endpoint will be based on viremia quantitation performed at the central laboratory. Resolution of viremia will be defined by the lower limits of quantitation (LLOQ) of the assays used (BKV, AdV, CMV, HHV-6, JCV are measured in the plasma, EBV is measured in peripheral blood mononuclear cells). Only participants who had viremia at randomization for each target virus will be included in the analysis.

Average daily bladder pain (ie, the participant's average bladder pain over the previous 24 hours) will be recorded daily for the first 6 weeks of the study and once weekly thereafter. The average daily bladder pain will be averaged for each week for the first 6 weeks and starting at Week 7, the single average daily pain score will be recorded. The applicable weekly measures will be summarized by treatment group over the 24-week study period. Only pain assessments

without use of prescription pain medications (not PRN or "as needed") or supportive bladder care will be used.

Time to global impression of hemorrhagic cystitis severity of none or mild, confirmed with 2 consecutive scores, will be analyzed similar to the key secondary endpoint. The analysis will include all the participants who exceed "mild" at randomization. If the scores at randomization are missing, a prior score will be used if available. Otherwise, the participant will not be included in the analysis. Time to resolution will be calculated from the date of randomization to the date of the first time reaching the global impression of hemorrhagic cystitis severity of non or mild, without use of prescription pain medications (not PRN or "as needed") or supportive bladder care. Participants not observed to achieve the threshold will be considered censored at their last follow up.

Cumulative days of supportive bladder care for HC, specifically continuous bladder irrigation and/or nephrostomy tubes, will be summarized by treatment group. In the analysis, cumulative days of supportive bladder care will include all days of such therapy for the entirety of the trial. Time to discontinuation refers to time from randomization to initial discontinuation of all supportive bladder care in participants who were receiving a supportive bladder care at randomization. Time to discontinuation of supportive bladder care for HC will be analyzed using Kaplan-Meier estimates, and treatment effect will be compared using stratified log-rank test and hazard ratio with stratified Cox proportional model.

HC-associated signs and symptoms other than bladder pain will be descriptively summarized. The signs and symptoms analyzed include urinary frequency, urinary urgency, constant need to urinate, and nocturia.

Incidence and time to recurrence of HC will be analyzed using Kaplan-Meier estimates, and treatment effect will be compared using stratified log-rank test and hazard ratio with stratified Cox proportional model. Only participants who have reached the HC resolution will be included in the analysis. Time to recurrence of HC refers to time from the HC resolution to the time when the initial Bedi grade to evaluate for recurrence demonstrates a Bedi Grade ≥2 with macroscopic hematuria.

Incidence and time to recurrence of bladder pain will be analyzed using the same methods. Only participants who have reached the bladder pain resolution will be included in the analysis. Time to recurrence of bladder pain refers to time from the bladder pain resolution to the time when the initial pain score exceeds "mild pain" without use of prescription pain medications or supportive bladder care.

The number of participants requiring RBC and/or platelet transfusions and the number of required RBC and/or platelet transfusions (measured in transfusion units/participant) will be summarized by treatment group.

Change in renal function as assessed by eGFR and number of days on dialysis for participants requiring dialysis will be summarized by treatment group.

Time to resolution of BK viruria will be analyzed using Kaplan-Meier estimates, and treatment effect will be compared using stratified log-rank test and hazard ratio with stratified Cox proportional model. Resolution of viruria is defined by the lower limits of quantitation of the assay used. Resolution of viruria is defined by the lower limits of quantitation of the assay used. Only the participants who had BK viruria at randomization will be included in the analysis. Time to resolution refers to the time from randomization to the initial resolution of viruria.

The numbers and proportions of patients with viremia and viruria with each target virus (ie, BKV, AdV, CMV, HHV-6, JCV, and/or EBV) over time for all the participants as well as for participants who are negative at randomization only.

Length of use of any pain medication(s) (IV, oral, or other), including antispasmodics anticholinergics, and beta-3-agonists, used for control of lower abdominal/bladder pain will be summarized as the total days on any pain medication for each participant.

The use of immunosuppressive agent(s) by specific agent during the study will be summarized by treatment group. The specific dosage information will be listed only.

Number of hospitalizations, number of ICU stays, and number of days of ICU care for any reason will be summarized by treatment group, and reasons will be listed by participant.

Use of antiviral therapies other than cidofovir with potential activity against at least one target virus will be summarized by specific agent during the study. Agents analyzed include foscarnet, ganciclovir, letermovir, maribavir, and valganciclovir. Rd

Overall survival, defined as time to death (from any cause) from the time of randomization in days, will be analyzed as displaying number of participants who died from any cause by week 24 and censored by week 24.

Incidence of relapse or progression of the primary malignancy will also be summarized by treatment group over the 24-week period.

Overall quality of life as measured by appropriate EQ-5D questionnaires will be summarized by treatment for each subdomain over time.

Global impression of change will be summarized by treatment over time.

